**A Comparative Study of Tubeless Percutaneous Nephrolithotomy With or Without Reverse Ureteral Catheter Insertion**

NCT number: NCT05574517  
Version number: V2.0  
Release date: October 8, 2022

1. Title: A comparative study of tubeless percutaneous nephrolithotomy with or without reverse ureteral catheter insertion.
2. Trial registration: Clinical Trial Registry (<https://www.clinicaltrials.gov>).
3. Version number and date: Version Number: V1.0 Version date: September 23, 2022.
4. Funding: Key Clinical Research Project of University of South China (No. USCKF201902K01).
5. Investigator and responsibilities: [name], deputy chief physician (study leader) : trial design, surgical implementation, protocol management, and process guidance; Research group postgraduate: data collection and analysis, article writing and publication.
6. Research background and principle: PCNL is the first-line treatment for renal calculi and upper ureteral calculi. With the development of minimally invasive urological endoscopic technology and the improvement of patients' medical requirements, it has become a consensus that PCNL surgery will develop in the direction of less trauma, more concise operation and more reasonable innovation. The emergence of tubeless PCNL (without indwelling nephrostomy tube) has been proved to be safe and effective in reducing postoperative discomfort, shortening hospitalization time and reducing hospitalization costs, so it has been paid more and more attention by clinical medical workers. Traditional tubeless PCNL usually requires placing the patient in the lithotomy position and retrograde insertion of the ureteral catheter under transurethral ureteroscopy, which is theoretically considered to be used to establish "artificial hydronephrosis" guided puncture and to prevent stones from falling into the ureter to form ureteral stone street. However, a large number of practices have found that the reverse insertion of ureteral catheter can cause many ureteral-related surgical complications. And for those who have had spinal injury, spinal deformity or large joint stiffness of the body of the patient, often can not swing the lithotomy position. At this time, without reverse insertion of ureteral catheter can show its unique advantages: simplify the operation steps, shorten the operation time, reduce the repeated operation of the ureter and thus

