reduce the risk of long-term ureteral stenosis. However, there are few reports on tubeless PCNL without reverse ureteral catheter insertion. With the continuous update of ultrasound equipment and the continuous progress of physician puncture technology, ultrasound-guided percutaneous renal puncture is less and less dependent on retrograde pyelography or artificial hydronephrosis. Therefore, we believe that for patients with certain hydronephrosis and little stone burden, it is theoretically feasible to perform tubeless PCNL without reverse insertion of the ureteral catheter.

7. Objective: The purpose of this study is to explore the safety and clinical efficacy of this new surgical method in the treatment of upper urinary calculi by combining the application of non-inverse insertion technique in the operation of tubeless PCNL, and to explore the applications of this new surgical method.

8. Experimental design: A two-arm parallel trial design was carried out. The participants who underwent tubeless PCNL without reverse insertion of a ureteral catheter were selected as the experimental group, and the participants who underwent traditional tubeless PCNL with reverse insertion of a ureteral catheter were selected as the control group.

9. Site: This was a single-center study conducted at the First Affiliated Hospital of the University of South China.

10. Inclusion and exclusion criteria: Inclusion Criteria: 1. Participants who met the the applications of PCNL surgery in the 2019 Chinese Guidelines for the Diagnosis and Treatment of Urological Diseases; 2. Participants who agree to undergo tubeless PCNL; 3. The participants' maximum diameter of the stone should be less than 3.5cm. Exclusion Criteria: 1. Confirmation by computerized tomography (CT) images and blood biochemical indicators of infectious stones or complex staghorn stones; 2. Obvious surgical contraindications, such as severe heart and lung insufficiency, abnormal coagulatory function; 3. Previous PCNL or nephrolithotomy, presence of an indwelling ureteral stent or nephrostomy tube before surgery; 4. Renal trauma or congenital malformation of the urinary system. If the following variations occurred during the operation: puncture difficulties in the

[figure not shown]

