12. Outcome measures: The primary clinical end point was the incidence of postoperative complications (including postoperative fever, bleeding, pain, and changes in renal function; Ureterostone street was formed after operation. Air - fluid chest after operation); The secondary clinical end points were operation time, hospital stay, hospital cost and stone clearance rate.

13. Recruitment flow chart:

14. Sample size: Combined with the number of outpatient calculi patients and the number of PCNL surgeries in our department of Urology each year, we planned to initially include 200 patients with renal and/or upper ureteral calculi who underwent tubular PCNL surgery in our hospital from October 2022 to December 2024, and randomly assigned at 1:1.

15. Participants: Patients with upper urinary stones attending the Urology Clinic of the First Affiliated Hospital of the University of South China were recruited.

16. Allocation sequence generation, allocation hiding, implementation methods: Computer random number generator was used. Participants with odd numbers were assigned to experimental group, where they underwent tubeless PCNL without

reverse insertion of a ureteral cathete. Participants with even numbers were assigned to control group and underwent tubeless PCNL with reverse insertion of a ureteral cathete. This process takes place in the operating room.

17. Blinding: In a single-blind approach, patients are told to participate in a clinical trial but are not informed about the specific intervention, while the person administering the intervention is clearly informed.

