18. Data collection: The measured data of all the required: 1. The demographic data, stone characteristics and preoperative baseline data, including the proportion of gender, age, body mass index (BMI) and basic diseases distribution, location, stones, stone maximum cross-sectional area, the longest diameter antler shape proportion and pelvic effusion width, partial side and puncture operation, etc. 2. Data of the main end points included: Postoperative fever and inflammation (temperature, preoperative blood leukocyte count difference after operation, neutrophils ratio difference, post-operative sepsis), postoperative bleeding (preoperative differential postoperative hemoglobin and hematocrit value and blood in the urine, subcapsular renal week or hematoma after operation, postoperative DSA guided by selective renal artery embolization bleeding), postoperative pain, postoperative analgesia drug demand, Mainly non-steroidal anti-inflammatory analgesic drugs), renal function changes (preoperative and postoperative serum creatinine difference), ureteral stone street formation rate and the incidence of gas and fluid chest (postoperative CT showed the presence of gas and fluid accumulation in the chest); Secondary end points included operation duration, length of hospital stay, hospitalization cost, and stone clearance rate. 3. Follow-up was conducted for 1 month after discharge, including: high fever, obvious pain and hematuria after discharge; Whether there is readmission; Whether to remove the double J tube as scheduled.

19. Statistical analysis plan: SPSS26.0 statistical software was used for analysis. Measurement data were expressed as mean  $\pm$  standard deviation ( $X \pm S$ ) and t-test was used. Enumeration data were expressed as frequency and percentage by  $X^2$  or Fisher exact test. Rank sum test was used for rank data.  $P < 0.05$  was considered

statistically significant.

20. Ethical approval: This trial was a human life science and medical study and was approved by the Medical Ethics Committee of the First Affiliated Hospital of the University of South China (No. : 2022110924001).

21. Informed consent: All participants enrolled in the study signed a surgical consent and a clinical trial informed consent to collect and use the medical behavior information and biological samples for the study.

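### The protocol gives ureteral harm from inserting the catheter as a reason for omitting it, but records no ureteral injury as an outcome

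*Protocol*

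**What the plan says.** - **Protocol, section 6 (background).** Two opposing ureteral effects are described. The catheter is held, in theory, "to prevent stones from falling into the ureter to form ureteral stone street". Against it, the section states that "the reverse insertion of ureteral catheter can cause many ureteral-related surgical complications". Omitting it is expected to "simplify the operation steps, shorten the operation time, reduce the repeated operation of the ureter and thus" to "reduce the risk of long-term ureteral stenosis".
- **Section 7 (objective).** The aim is general: to explore the safety and clinical efficacy of the method.
- **Section 12 (outcomes).** "The primary clinical end point was the incidence of postoperative complications (including postoperative fever, bleeding, pain, and changes in renal function"; the list goes on: "Ureterostone street was formed after operation. Air - fluid chest after operation". The secondary endpoints are operation time, hospital stay, cost and stone clearance.
- **Section 18 (data collection).** The main-endpoint data cover fever and inflammation, bleeding, pain and analgesic need, creatinine change, and "ureteral stone street formation rate and the incidence of gas and fluid chest". Follow-up at 1 month after discharge asks about high fever, pain, hematuria, readmission and removal of the double J tube.
- **Section 10 (end of the exclusion criteria).** Certain variations during the operation are shown in the flow chart but left out of the final analysis. They include a stone street that needed ureteroscopic treatment after a change of position. As far as the broken text can be read, they also include difficult punctures converted to catheter guidance.

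**The concern.** The randomised contrast is insertion versus omission of a ureteral catheter, and the protocol names a possible ureteral harm on each side. Only the harm linked to omission, stone street, has a place among the outcomes and the data items. A ureteral injury caused by insertion has none. The primary endpoint is also confined to postoperative complications, whereas section 11 places insertion at the start of the operation, under ureteroscopy. An injury seen at that moment is not a postoperative event.

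What is at stake is whether the trial can answer its own safety question. This cannot be left to a statistical analysis plan: no analysis can recover an event that was never recorded.

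**Working it through.** **Step 1. Follow each ureteral effect named in section 6 through the protocol.**

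- Stone street (possible harm of omission): in the primary endpoint, yes; in the section 18 data, yes, as a rate.
- Ureteral complications of insertion (harm of the control procedure): not in the primary or secondary endpoints, not in the section 18 data, and not in the 1-month follow-up.
- Long-term ureteral stenosis (claimed benefit of omission): no endpoint and no data item, and follow-up ends 1 month after discharge.
- Shorter operation (claimed benefit of omission): a secondary endpoint, so this part of the rationale is tested.

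**Step 2. Is there a figure to reproduce?** No. The 200 patients (1:1, so 100 per arm) in section 14 come from clinic and surgery volume, and no event rate, effect size, power or margin is given. Any magnitude below is an illustration.

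**Step 3. Illustration on assumed rates.** Let b be the rate of all other complications in both arms, s the added stone street rate in the no-catheter arm only, and u the ureteral injury rate in the catheter arm only, acting independently. An arm's rate is 1 − (1 − b)(1 − x), with x = s or u. Differences are new method minus control.

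- Components as listed: s(1 − b). For s = 2% to 5% and b = 10% to 30%, this runs from 0.02 × 0.70 = +1.4 points to 0.05 × 0.90 = +4.5 points.
- Ureteral injury not counted: u(1 − b). For u = 2% to 10%, this runs from 0.02 × 0.70 = 1.4 points to 0.10 × 0.90 = 9.0 points.
- Difference if injury were also counted: (1 − b)(s − u). This runs from 0.90 × (0.02 − 0.10) = −7.2 points to 0.90 × (0.05 − 0.02) = +2.7 points, and is 0 when s = u.

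**Step 4. Allow for the section 10 exclusions.** If every added stone street led to an excluded conversion, the listed difference would fall from +1.4 to +4.5 points to 0. If stone streets appear only after the operation, the exclusion does not touch them and the whole difference stays. The protocol does not say how the events would divide. Excluding punctures converted to catheter guidance removes further failures of the no-catheter method, in unknown number.

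**The case against.** The strongest points on the other side are these.

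1. *The endpoint list is open.* Section 12 says *including*, and section 18 introduces the main-endpoint data in similar terms. A consequential injury could also surface as fever, sepsis, hematuria, pain, a creatinine rise or readmission. This stands in part: some insertion harm would be picked up indirectly. But those signs are non-specific and cannot attribute harm to the ureter. An open list also does not create a data item, or make an intra-operative injury postoperative.

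2. *The direction of bias.* A reader might infer that the primary endpoint is tilted against the new method. The documents do not support that as a net statement. The omission alone works that way if insertion causes injuries not otherwise counted, but the section 10 exclusions work in favour of the new method, and no rates are given to weigh one against the other.

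3. *The rationale as a whole.* A reader might infer that the trial cannot test its rationale. That goes too far: operation time is measured, and the stated objective is general. Only the ureteral-injury and stenosis parts go untested.

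4. *A false conclusion of harm.* A reader might also infer that the trial would declare more ureteral complications with the new method. No separate comparison of ureteral complications is described, and 3 versus 1 stone streets in 100 per arm gives a Fisher p of 0.62.

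5. *The illustration.* It sets injury in the new arm to zero, although section 11 passes a guide wire and a double J tube down the ureter in both arms. This is fair, and a reason to record injury in both.

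6. *Putting injury or failed catheterisation into the primary endpoint.* Failed catheterisation is by design a control-arm event, and its counterpart, failed puncture without a catheter, is excluded under section 10. Adding it to the primary would create a new imbalance. This stands, and the fix leaves the primary alone.

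**Conclusion.** The concern holds in a limited form. The omission itself is read directly from sections 6, 12 and 18 and needs no assumption: ureteral harm from insertion helps to justify the trial, and nothing in the outcomes or data list records it. The comparison can therefore register a harm of omitting the catheter, but cannot directly show or refute the ureteral-injury benefit. Nor can follow-up of 1 month after discharge support a claim about long-term stenosis.

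The magnitude rests wholly on assumed rates and on independence of the components, with injury confined to controls. The illustration shows only that the uncounted events could be as large as the stone street difference or larger. It does not establish which arm the protocol as a whole favours. The change is worth making because it is cheap and the information cannot be obtained later.

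**What to change.** - Keep the primary endpoint as it is.
- Add to sections 12 and 18 a separately reported safety outcome, *ureteral injury (intra-operative or postoperative)*, recorded in both arms from the operative note, the existing imaging and the 1-month follow-up.
- Report injuries that needed action or had clinical consequences apart from minor findings seen only at ureteroscopy.
- Report failed catheterisation descriptively for controls, outside the primary endpoint, next to the conversions in the no-catheter arm, so that procedural failures on both sides are visible.
- State that no conclusion on long-term stenosis will be drawn from the 1-month follow-up.

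The cost is a line in each of the two sections and one field on the operative form, with no extra procedure. The downside is some unequal detection, since only controls have routine ureteroscopy. Separating consequential injuries from minor findings reduces this but does not remove it, and the report should say so.

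### Hydronephrosis and stone burden, on which section 6 says the new method depends, are neither balanced by the design nor used in the unadjusted tests of section 19 (minor)

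*Protocol*

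**What the plan says.** - **Size and ratio (protocol, section 14).** The plan is for 200 patients, "and randomly assigned at 1:1".
- **Procedure (section 16).** "Computer random number generator was used. Participants with odd numbers were assigned to experimental group"; "Participants with even numbers were assigned to control group"; "This process takes place in the operating room". No block, stratum, minimisation or fixed arm total is described here or elsewhere. The section does not say whether the numbers are independent draws, a shuffled list or participant serial numbers.
- **Factors tied to the method (section 6).** The authors consider the technique feasible "for patients with certain hydronephrosis and little stone burden".
- **Eligibility (section 10).** Stone diameter must be below 3.5 cm and complex staghorn stones are excluded. There is no criterion on hydronephrosis.
- **Baseline data (section 18).** Pelvic effusion width, longest stone diameter and maximum stone cross-sectional area are collected.
- **Analysis (section 19).** The section names the t-test, the chi-square or Fisher exact test and the rank sum test, at P < 0.05. It names no covariate.

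**The concern.** The protocol itself identifies two patient characteristics that should decide how well the new method works. It measures both before surgery and then uses neither in the allocation nor in the stated analysis. Eligibility narrows stone size but leaves the degree of dilation open. If one arm happens to receive more poorly dilated kidneys or larger stones, and these raise complication risk, the unadjusted estimate moves with that imbalance. At stake are some precision and the credibility of the estimate from this one sample. The validity of the test is not in question.

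**Working it through.** **Inputs.** From the protocol: N = 200 and ratio 1:1 (section 14), odd/even assignment (section 16), threshold 0.05 (section 19, taken as two-sided). The protocol gives no event rate, covariate prevalence or prognostic effect, so these are assumed: prevalence q = 30–50%, effect of the factor on complication risk 20 points, overall complication rate 20%.

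**1. Does the odd/even rule give 1:1?** With independent draws and P(odd) = 0.5, the expected split is 200 × 0.5 = 100 per arm, so the stated ratio is reproduced as an allocation ratio. The realised split varies. From Binomial(200, 0.5), P(exactly 100:100) = 0.056, the 95% range for one arm is 86 to 114, and P(90:110 or worse) = 0.179.

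**2. What does unequal arm size cost?** The variance ratio at 86:114 is (1/86 + 1/114) / (2/100) = 1.020, so the variance is 2% larger. At 90:110 the relative efficiency is 4 × 90 × 110 / 200² = 0.99. Averaged over the binomial split, power for 30% vs 15% (assumed) is 0.720, against 0.722 at exactly 100:100. Arm size is therefore not the issue.

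**3. Chance imbalance in one baseline factor.** With 100 per arm, SD = √[q(1 − q) × 2/100].

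| q | SD | P(gap ≥ 10 points) |
|---|---|---|
| 30% | √(0.21 × 0.02) = 0.065 | 0.12 |
| 50% | √(0.25 × 0.02) = 0.071 | 0.16 |

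**4. What would such a gap do?** Shift in the risk difference = 0.10 × 0.20 = 0.02, or 2 points. The standard error of the risk difference at a 20% rate is √(2 × 0.20 × 0.80 / 100) = 0.0566. The ratio is 0.02 / 0.0566 = 0.35 standard errors.

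**5. Is the unadjusted test still valid?** In simulation under simple randomisation, the chi-square test rejected in 0.050 of null trials with a common 20% risk. It rejected in 0.051 when a factor of 30% prevalence, with risks of 35% and 15%, was left unstratified. The type I error stays nominal.

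**6. What does adjustment gain?** With an assumed 40% prevalence and a 20-point effect of the factor, adjustment raised simulated power from about 67% to about 69% under simple randomisation. Stratifying the allocation as well added nothing further.

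**The case against.** The strongest reply is that simple randomisation needs no repair. It balances every factor in expectation, and the standard error of the unadjusted test already allows for chance imbalance. This stands, and it is why the point is minor.

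Three stronger readings may tempt a reader, and the protocol supports none of them.

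- *Section 16 breaks the 1:1 promise of section 14.* It does not. Section 14 states a ratio and does not promise 100 patients in each arm; an equal-chance draw honours that ratio.
- *Allocation is plainly unrestricted.* This is only the natural reading, because the numbers are not defined. A random permutation of 1 to 200 would give exactly 100:100. Parity of serial numbers would amount to alternation, nearly balanced in size and time but predictable. The arm-size figures above apply to independent draws only.
- *An imbalance could not be told apart from the effect of omitting the catheter.* This overstates it, since the covariates are recorded and any imbalance can be seen and adjusted for.

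A learning effect over the 27 months of recruitment by one operator is conceivable, but the protocol gives no figure for it. Fixing the totals at 100/100 would help little. Among the first 40 patients, P(26:14 or worse) falls only from 8.1% to 5.1%, and the 12–16% in step 3 does not change, because it already takes 100 per arm.

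It can also be said that covariate adjustment belongs in a separate SAP, which may exist. That is fair. But section 19 carries the heading of a statistical analysis plan and states the tests, so the tests it states can be commented on.

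**Conclusion.** The point holds as a minor weakness of the stated analysis, not as an error in the randomisation. The two factors that section 6 links to the method are left to chance in the design and omitted from the tests in section 19, although section 18 provides the data. The likely harm is modest: a 12–16% chance per factor of a gap of 10 points or more, and a shift of about 0.35 standard errors if that happens. The prevalence, the 20-point effect and the 20% complication rate are assumptions; a weaker prognostic factor would make the shift proportionally smaller. The figures also take all 200 patients as analysed. Section 10 removes some after assignment, which would make chance gaps somewhat more likely.

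**What to change.** In section 19, or in the SAP if there is one, pre-specify before outcome data are examined that the primary complication comparison is adjusted for baseline pelvic effusion width and stone size. A stratified risk difference or a logistic regression would serve; use linear models for the continuous outcomes. Fix any cut-offs in advance and keep the unadjusted tests as supportive. The covariates are already collected, so the cost is a few sentences and slightly more analysis work.

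Add a sentence to section 16 saying how the numbers are generated and linked to participants.

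Stratified or blocked randomisation is optional. If it is used, take stone size rather than stone site as the stone factor, because section 6 refers to burden. Use concealed, mixed block sizes, since the operator sees past assignments and could otherwise predict some of the next ones, and include the strata in the analysis.

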lithotomy position and inverse insertion of ureteral catheter-guided puncture, a finding that pyonephrosis demanded the treatment of nephrostomy, channel bleeding that was required to maintain a nephrostomy tube, larger residual calculi that needed a nephrostomy tube for a secondary surgery, or a ureteral stone street that necessitated ureteroscopic lithotomy by changing to the lithotomy position; Or incomplete postoperative clinical data will be recorded by the study recruitment flow chart, but not included in the final data analysis.

11. Intervention measures: a. According to the randomization, the same associate chief urologist performed tubeless PCNL without reverse ureteral catheter or traditional reverse ureteral catheter; B. During the perioperative period, participants were given comprehensive blood biochemical examination and imaging evaluation, and antibiotics (second-generation cephalosporins or penicillins) were prophylactic. Participants with hypertension, diabetes and other comorbidities were given relevant drugs to control the tolerable level of surgery. C. Implementation process of tubeless PCNL without reverse insertion: After detaining urethral catheter for patients with tracheal intubation general anesthesia, to take a prone position, suffer renal biopsy under ultrasound guided look straight into the target under the calyces, syringe after water injection and suction is smooth, the guide wire guided by micro fascia dilator (Fr16 or Fr18) continuous build percutaneous renal channel expansion, step by step with holmium laser remove all break "can see the stone", A 6Fr double J tube was placed antegrade under the guidance of the guide wire, and no stone residue was detected. No active bleeding was observed in the channel during the withdrawal of the lens. The implementation process of traditional reverse insertion of tubeless PCNL was as follows: the participants were intubated for general anesthesia. First, the ureteral catheter was inserted under transurethral ureteroscopy in the lithotomy position and fixed on the catheter. The process of establishing percutaneous renal channel under ultrasound guidance and stone removal was the same as that of tubeless PCNL without the use of a retro-inserted ureteral catheter. Double J tubes were placed antegrade under the guidance of guide wire, and the

skin incision was sutured and closed after no residual "visible stones" and no active bleeding under endoscopic observation.

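### Section 17 masks patients only, and nothing masks those who record pain, analgesic demand and haematuria, which count towards the primary endpoint without a scale or threshold

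*Protocol*

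**What the plan says.** Section 17 (Blinding) names two parties. Patients are masked: "In a single-blind approach, patients are told to participate in a clinical trial but are not informed about the specific intervention". The operator is not: "while the person administering the intervention is clearly informed". It mentions nobody else.

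Section 5 (Investigator and responsibilities) gives one role both the recording and the analysis: "Research group postgraduate: data collection and analysis, article writing and publication". It does not say whether that role knows the allocation.

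Section 12 (Outcome measures) defines the primary endpoint as an incidence: "The primary clinical end point was the incidence of postoperative complications (including postoperative fever, bleeding, pain, and changes in renal function", followed by steinstrasse (stone street) and air or fluid in the chest.

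Section 18 (Data collection), item 2, lists what is recorded for it. Some entries are measured, for example "Postoperative fever and inflammation (temperature, preoperative blood leukocyte count difference after operation, neutrophils ratio difference, post-operative sepsis". Bleeding mixes laboratory values with an ungraded observation: "preoperative differential postoperative hemoglobin and hematocrit value and blood in the urine". Pain appears as "postoperative pain, postoperative analgesia drug demand". No scale, grade or cut-off is given for pain, analgesic demand or blood in the urine.

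Section 11 (Intervention measures) ends both operations in a similar state. For the control arm it says "Double J tubes were placed antegrade under the guidance of guide wire", and the experimental arm also receives an antegrade double J tube. As a tubeless procedure, neither arm keeps a nephrostomy tube.

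**The concern.** An incidence needs a yes-or-no decision for every patient. For haemoglobin, creatinine or a CT finding, the measurement leaves little room for opinion. For pain, analgesic demand and visible blood in the urine, someone must ask, grade and decide whether an event has occurred, and the protocol gives that person no rule. If that person knows the arm, borderline cases may be settled differently in the two arms, and the comparison would read the difference as a treatment effect.

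The plan does nothing to prevent this. Section 17 is where masking is fixed, and it stops at the patient. Two other features make it easy to learn the arm. Section 16 sends odd numbers to the experimental group and even numbers to the control group, so the number itself reveals the arm if it is carried on the study record. Section 18 collects operation time and outcomes together, while the control operation begins with ureteroscopic catheter insertion in the lithotomy position, so an operative record shows which procedure was done. Section 22 codes personal identity, not allocation.

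**Working it through.** **Textual check**

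| Item | Where recorded | Who or what decides it |
|---|---|---|
| Temperature, leukocyte and neutrophil differences | Section 18, item 2 | Instrument or laboratory |
| Haemoglobin, haematocrit, creatinine differences | Section 18, item 2 | Laboratory |
| Chest air or fluid | Section 18, item 2 | CT |
| Embolization | Section 18, item 2 | Recorded procedure |
| Pain, analgesic demand, blood in the urine | Section 18, item 2 | Patient report and staff judgement, no rule |
| High fever, obvious pain, haematuria after discharge | Section 18, item 3 | Follow-up item, not listed under the main end points |

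The exposed primary components are therefore the three in the fifth row.

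**Illustration of size.** The protocol gives no event rate, effect size or power (section 14 justifies 200 patients by clinic volume), so there is no figure of its own to reproduce.

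Inputs from the protocol: 200 patients at 1:1, hence n = 100 per arm (section 14); chi-square test and P<0.05 (section 19), taken here as two-sided and uncorrected. Assumptions: a true rate of 20% in both arms, with a fraction f of events going unrecorded in one arm, so that its recorded rate is 0.20 × (1 − f).

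For counts x and y, with p̄ = (x + y)/200, the statistic is χ² = ((x − y)/100)² / [p̄(1 − p̄) × 2/100]. The chance of P<0.05 is the sum of Bin(x; 100, p₁) × Bin(y; 100, p₂) over all pairs with χ² > 3.841. By exact enumeration:

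| Unrecorded in one arm | Recorded rates | Chance of P<0.05 |
|---|---|---|
| 0% | 20% v 20% | 5.1% |
| 10% | 20% v 18% | 6.7% |
| 20% | 20% v 16% | 11.6% |
| 25% | 20% v 15% | 15.6% |

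The 20% rate is itself an assumption. A normal approximation to the same test gives 6.5% and 11.4% for 10% and 20% under-recording at a true rate of 20%, 7.6% and 15.9% at 30%, 9.0% and 21.7% at 40%, and 10.9% and 29.4% at 50%.

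**Dilution in a composite.** Suppose the endpoint is any complication, and the remaining components are recorded without bias, are independent of this one and occur in a proportion q. The recorded rate is then 1 − (1 − p)(1 − q). For the 25% case:

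- q = 20%: 1 − 0.80 × 0.80 = 36% v 1 − 0.85 × 0.80 = 32%. The chance of P<0.05 is 9.2%, against 5.0% with no shift.
- q = 40%: 1 − 0.80 × 0.60 = 52% v 1 − 0.85 × 0.60 = 49%. The chance is 7.8%, against 5.6% with no shift.

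**The case against.** The strongest reply is that the main safeguard is already in place. Pain is felt and reported by the patient, analgesic demand is at least partly prompted by the patient, and the patient is masked. Most of the other primary items come from instruments, the laboratory or imaging. This stands as mitigation. It does not cover how staff ask about pain, grade it, respond to it and write it down, or how blood in the urine is judged.

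A second reply is that coding of arms for the analyst is commonly left to a SAP, which is not at hand. That is fair, and its absence is not counted as an error here. Who is masked during outcome recording is a design matter, however, and section 17 is where this protocol settles it.

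Three stronger readings are tempting, and the documents do not support them.

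- A reader might infer that the postgraduate is unmasked. The protocol is silent. The single-blind label and the features of sections 16 and 18 make knowledge of the arm likely, but that remains an inference.
- A reader might count fever, pain and haematuria reported after discharge as primary components. Section 18 lists them as follow-up, apart from the main end points, and primary fever is recorded through temperature and laboratory values.
- A reader might expect severe damage to the primary test. If the recorded rate fell from 20% to 10%, the chance of P<0.05 on that component would be 51.8%. That requires half of one arm's events to go unrecorded, which nothing in the protocol suggests, and it tests one component alone. In the any-complication calculation the same shift gives 23% to 15%.

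Finally, masking on the ward may be imperfect. In the control arm the ureteral catheter is fixed to the urinary catheter, and the protocol does not say when it is removed, so a visible sign of the arm could remain.

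**Conclusion.** The point holds as a gap in the design. Patients are the only masked party, nothing separates outcome recording or analysis from knowledge of the arm, and three primary components rest on undefined judgement. The exposure is real but limited. With 100 per arm and an assumed true rate of 20%, under-recording of 10% to 25% in one arm raises the chance of a false significant result on the affected component from 5.1% to between 6.7% and 15.6%. It is higher if the component is commoner. On an any-complication endpoint, the 25% case gives about 8% to 9% if the other components occur in 20% to 40%. The event rates, the degree of under-recording and the independence of components are all assumptions, and the documents fix none of them. The change should be made because it is cheap; the figures do not show that the result would be invalid without it.

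**What to change.** Amend section 17 to state that:

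- the existing staff who record pain, analgesic demand and haematuria do not attend the operation and have no access to the allocation list, the odd/even number or the operative note;
- operative data, such as operation time and intra-operative events, are entered in theatre on a separate form;
- the analysis file carries arms coded A and B until the primary analysis is final.

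The cost is protocol wording, a split data form and the discipline of keeping operative and outcome records apart. No new assessor or procedure is needed, since only form routing and access to the allocation change. Feasibility is a judgement that the protocol does not state. The A/B coding can be done in any case. Masking on the ward works only as far as no visible sign of the arm remains after surgery, so section 17 should say how far it can be achieved given the control arm's ureteral catheter.
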